3.8.3 Analyses of the Exploratory Efficacy Endpoints

A high-contrast, black and white image showing a series of horizontal bands. The bands are mostly black, with thin white horizontal lines separating them. The right edge of each band is irregular, showing a jagged, stepped pattern that tapers off towards the right. The overall effect is reminiscent of a digital signal or a stylized landscape.

3.8.4 Subgroup Analyses

3.9 Safety Analysis

All safety data analyses will be conducted using the Safety Analysis Set.

3.9.1 Adverse Events

All adverse events will be coded using the Medical Dictionary of Regulatory Activities (MedDRA) Version 19.1 and will be classified by MedDRA system organ class (SOC), high level group term (HLGT), high level term (HLT), and preferred term (PT). Analyses of adverse events will be performed using the Safety Analysis Set.

Treatment emergent adverse events (TEAEs) are any adverse events occurring or worsening in severity after the first administration of study medication. The following imputation rules will be used for missing or incomplete AE start dates:

- Missing AE start day:
 - If the partial date contains a different month from the date of first study dose, then impute it as the first day of the month.
 - If it contains the same month as the date of first dose, then impute it as date of first dose.
- Missing AE start day and month:
 - If the partial date contains a different year from the date of first dose, then impute the missing day and month as Dec 31.
 - If it contains the same year as the date of first dose, then impute the missing day and month as day and month of first dose.
- Completely missing AE date:
 - Impute the missing date as the date of first dose.

The TEAE incidence will be presented by treatment group for all subjects in the Safety Analysis Set. The number and percentage of subjects who experience at least one TEAE and the number and percentage of subjects who experience at least one TEAE within each specific SOC and PT will be presented by treatment group (placebo, combined OV101 and separate dose groups). Additionally, the incidence of TEAE within each specific SOC, HLGT, and PT and specific SOC, HLT, and PT will be presented. The 95% CIs will be displayed for the frequency of TEAEs. Treatment-related AEs will be considered those at least possibly related to investigational product based on the investigator's assessment. The number and percentage of subjects reporting serious AEs, treatment-related AEs, and AEs leading to treatment discontinuation will also be summarized for each treatment group by MedDRA SOC and PT.

The AEs of Special Interest include Dizziness, Somnolence, Nausea, Vomiting PTs, and will be reported separately.

All adverse event data including baseline adverse events will be displayed in subject data listings.

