3.6 Prior and Concomitant Medications

Therapies started and stopped prior to the start of study treatment are referred to as prior therapies. Therapies that started prior to treatment and continued on treatment as well as those that started during treatment are referred to as concomitant therapies. In order to define whether a medication with missing start or stop dates is a concomitant medication, refer to the following additional criteria.

- if both the start and stop dates of a particular medication are missing, that medication will be considered concomitant;
- if the start date of a medication is missing and the stop date of that medication falls on or after the dose date, that medication will be considered concomitant;
- if the start date of a medication is missing and the stop date of the medication is prior to the dose date, that medication is considered *not* concomitant;
- If the start date of a medication is prior to the dose date and the stop date of the medication is missing, that medication is considered concomitant.

Prior and concomitant medications will be coded using WHO Drug Dictionary Enhanced version June 2016 and will be classified by Anatomical Therapeutic Class (ATC) level 4 and preferred term (PT) for the Safety Analysis Set. For the presentation of concomitant medications, the ATC level 4 terms will be sorted alphabetically, and within ATC level 4 term, the PT will be used and presented by decreasing total frequency overall.

Frequencies and percentages of subjects using each concomitant medication will be presented for the Safety Analysis Set overall, and by treatment group.

All medication use will be listed regardless of the timing of the start of the medication.

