10.1.3.1 Screening Period (Day -28 to Day 0)

After obtaining a signed informed consent form (ICF) from the parent or legally authorized caregiver and assent as appropriate from the potential subject, individuals with AS will begin the study screening procedures for eligibility including clinical and laboratory evaluation and all measurements used for efficacy assessment (sleep, motor function, and behavior). Assent will be obtained if the investigator believes that the subject can provide it depending on the subject's intellectual ability, but assent may not be relevant for non-verbal subjects.

Investigators will explain to caregivers the necessity to discontinue the intermittent use of sleep medication and not to introduce new medication during the study.

Study centers will request a subject registration and treatment code centrally generated by an Interactive Web Response System (IWRS) (Section 12.3). No subject may begin treatment prior to assignment of a unique identification number (registration) and randomization. Any subject identification numbers that are assigned will not be reused, even if the subject does not receive treatment.

Screening laboratory assessments will be performed.

Caregivers will also be asked to sign a separate ICF for the subject to provide an additional blood sample (1 tube) at Baseline (and on Day 84 [Section 10.1.3.2]) to permit purification of DNA and plasma to enable identification of secondary pathogenic gene variants and allow for metabolic profiling. Those not consenting to this will still be eligible for the main study.

All subjects will be screened for participation in the study up to 28 days prior to the first dose administration. Subjects who meet all criteria can be randomized at any time during the screening period. The screening assessments are listed in Table 1.

The caregiver will be provided with an e-Diary for documenting sleep and subject's seizures.

During the screening period, it will be determined by the Investigator whether or not the caregiver and subject are able to complete all questionnaires and assessments that require their contribution to assess their ability to comply with study procedures.

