16.1 Adverse Events

16.1.1 Definitions

The definitions for TEAEs, AEs, and SAEs are given below. The Principal Investigator is responsible for ensuring that all study center staff are familiar with the content of this section. Any AE experienced by the subject between the screening visit (Day -28) and up to completion of the follow-up period after the last administration of study drug (Day 98 follow-up phone visit) must be recorded on the eCRF, regardless of the severity of the event or its relationship to study treatment.

Adverse Event (AE)

An AE is defined as any untoward medical occurrence in a clinical investigation subject, administered a pharmaceutical product, and which does not necessarily have a causal relationship with this treatment. An AE can therefore be any unfavorable and unintended sign (including an abnormal laboratory finding), symptom or disease temporally associated with the use of a medicinal (investigational) product, whether or not related to the medicinal (investigational) product.

Determination of whether an abnormal laboratory value meets the definition of an AE will be made by the investigator. Although abnormal laboratory values are typically not considered AEs, the following considerations may result in an abnormal laboratory value being considered an AE:

- A laboratory test result meets the criteria for an SAE
- A laboratory test result requires the subjects to receive specific corrective therapy
- A laboratory abnormality that the investigator considers to be clinically significant

Any intolerance that triggers a dose reduction during the titration period must be documented as an AE.

Treatment-Emergent Adverse Event (TEAE)

A treatment-emergent adverse event (TEAE) is defined as an AE with an onset that occurs after receiving study drug (AE start date \geq first dose date) and within 30 days after receiving the last dose of study drug (AE start date minus last dose date \leq 30), or an AE that occurs pre-treatment but worsens post treatment.

Serious Adverse Event (SAE)

An SAE is any untoward medical occurrence that at any dose:

- Results in death

- In the view of the investigator, places the subject at immediate risk of death (a life-threatening event); however, this does not include an event that, had it occurred in a more severe form, might have caused death

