16.1.1.6 Reporting of Serious Adverse Events

Investigators and other study center staff must inform appropriate [REDACTED] representatives of any SAE that occurs (whether or not attributable to the study drug) in the study within 24 hours (i.e. immediately but no later than the end of the next business day) or when he

or she becomes aware of it. It is the investigator's responsibility to ensure that SAE reporting procedures are followed appropriately.

All SAE reports must be faxed to the following number within 24 hours:

[REDACTED]
[REDACTED]
[REDACTED] [REDACTED]
[REDACTED] [REDACTED]
[REDACTED]
[REDACTED]
[REDACTED] [REDACTED]
[REDACTED] [REDACTED]
[REDACTED] [REDACTED]
[REDACTED]

In a study-related medical emergency situation, when assigned Medical Monitors for a study cannot be reached by a caller, an on-call Physician can be reached 24 hours per day, 7 days per week via the [REDACTED]

[REDACTED] [REDACTED]

(chargeable telephone number allowing a global reach from both landlines and mobile phones)

[REDACTED]

On this internet page, a list of country-specific toll-free telephone numbers is provided. It should be noted that not all countries globally have access to toll-free numbers as indicated on the "24/7 Medical Help Desk" index. Countries without toll-free numbers need to dial the chargeable number as indicated above. Furthermore, toll-free numbers are not available from mobile phones.

The [REDACTED] will work with the investigator to compile all the necessary information and ensure that the appropriate Ovid Therapeutics Inc. representative receives a report within one day (24 hours) for all fatal and life-threatening cases and within 5 days for all other SAEs.

Follow-up information on SAEs must also be reported by the investigator within the same time frames.

If a non-serious AE becomes serious, this and other relevant follow-up information must also be provided to [REDACTED] within one day as described above. For a non-serious AE that become serious but which is not fatal or life-threatening a report should be received within 5 days.

The following variables will be recorded for each AE: verbatim/AE description, time and date for AE start and stop, maximum intensity, seriousness, causality rating, whether or not the AE caused the subject to discontinue, and the outcome.

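### SAP 3.9.1 can count an adverse event that ended before dosing as treatment-emergent, and it drops the protocol's 30-day limit on TEAEs without listing the change

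*SAP*

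**What the plan says.** The protocol synopsis (statistical methods) names TEAE incidence as the primary endpoint.

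SAP 3.9.1 gives the working definition: "Treatment emergent adverse events (TEAEs) are any adverse events occurring or worsening in severity after the first administration of study medication". It then has five imputation branches for incomplete AE start dates:

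- Day missing, month of first dose: "If it contains the same month as the date of first dose, then impute it as date of first dose".
- Day missing, any other month: first of that month.
- Day and month missing, year of first dose ("If it contains the same year as the date of first dose"): first-dose date.
- Day and month missing, any other year: 31 December of that year.
- Nothing known: "Impute the missing date as the date of first dose".

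Three of the five therefore give the first-dose date, and none refers to the AE stop date. Protocol 16.1.1.6 requires "time and date for AE start and stop" for every AE, and protocol 16.1.1 starts AE recording at the screening visit.

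Protocol 16.1.1 defines a TEAE differently: onset on or after first dose and no more than 30 days after last dose, or a pre-treatment event that worsens. SAP 3.11 (Changes from Protocol), in its published text, covers the caregiver description, the compliance threshold, the ABC-I at clinic visits, the hypothesized effects and the primary comparisons. It says nothing about TEAEs.

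**The concern.** There are two separate problems.

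1. Setting an uncertain onset to the first dose is a cautious and common choice when the timing is truly unknown. It is not cautious when the stop date proves that the event was over before dosing. The rule then produces an impossible record and puts a pre-treatment event into the primary endpoint. That raises a SOC/PT row, and also the count of subjects with any TEAE if it is that subject's only event.

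2. The SAP and the protocol define the primary endpoint over different time windows. Programmers working from the two documents could produce different SOC/PT rows from the same data. SAP section 1 undertakes to identify substantial differences from the protocol, and protocol 17.2 asks for an amendment when an endpoint definition changes in a major way.

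**Working it through.** **The plan's own figure.** Protocol 17.1 gives a 95% CI half-width of 17% for a 25% incidence with 25 per group, and 19% with 20. The formula 1.96 × √(p(1−p)/n) gives 1.96 × √(0.25 × 0.75/25) = 16.97% and 1.96 × √(0.25 × 0.75/20) = 18.98%. Both reproduce, so the arm sizes and the scale of precision are as stated.

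**Part 1: the imputation rule**

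*Example.* First dose 20 March, AE start recorded as March, AE stop 10 March. The same-month branch imputes 20 March, which is 20 − 10 = 10 days after the event ended. The event is then a TEAE.

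*The same question elsewhere in the SAP.* For medications, SAP 3.6 covers the case "if the start date of a medication is missing and the stop date of the medication is prior to the dose date" and classes the medication as not concomitant. SAP 3.9.1 has no counterpart for AEs.

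*Effect of one subject.* 1/25 = 4 points; 1/20 = 5 points. Clopper-Pearson limits are the 2.5% point of Beta(x, n−x+1) and the 97.5% point of Beta(x+1, n−x):

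| Count | Incidence | Exact 95% CI |
|---|---|---|
| 6/25 | 24% | 9.4–45.1% |
| 7/25 | 28% | 12.1–49.4% |

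*How much pre-dose time the same-month branch reaches.* Screening may last 28 days but can be shorter (protocol 10.1.3.1: "Subjects who meet all criteria can be randomized at any time during the screening period"). Assume first doses spread evenly from 29 January 2017 to 8 April 2018. These limits come from the synopsis: first visit in the first quarter of 2017 (1 January + 28 days), and last visit in the second quarter of 2018 (Day 84 on 30 June). Count the L days before dosing that fall in the first-dose month:

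| L (days) | Mean days in first-dose month | Share |
|---|---|---|
| 28 | 14.5 | 52% |
| 14 | 10.4 | 74% |
| 5 | 4.5 | 90% |

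These are shares of calendar days, not error rates. An error also needs an incomplete start date and a stop date before dosing.

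**Part 2: the 30-day limit**

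Routine AE recording ends at the Day 98 call. The definitions can differ on those events only if last dose + 30 is before Day 98, that is, last dose before 98 − 30 = Day 68 (Day 66 to 70 with the ±2-day call window). The extra days counted by the SAP are 98 − (last-dose day + 30):

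| Last dose (day) | 7 | 14 | 28 | 43 | 57 | 68 |
|---|---|---|---|---|---|---|
| Extra days | 61 | 54 | 40 | 25 | 11 | 0 |

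These are maxima. They need follow-up to Day 98, which protocol 13.1.2 asks for after early discontinuation only where feasible.

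For a completer with last dose on Day 84 the limit is 84 + 30 = Day 114, so the definitions agree on everything recorded by Day 98. They can part only on late reports. Protocol 16.1.1.4 collects the event behind a death up to 60 days after last dose (84 + 60 = Day 144), so such an event starting on Days 115 to 144 is a TEAE under the SAP but not under the protocol. Protocol 16.1.1.2 likewise takes in related SAEs learned of after follow-up.

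**Interaction with the 31 December branch.** Under the SAP's open window this branch changes no planned count. With the 30-day limit restored, it would. The latest first dose in 2017 is 31 December; Day 87 (Day 84 plus the 3-day window) is 27 March 2018, and 30 days later is 26 April 2018. Every AE dated only 2018 in a subject first dosed in 2017 would be imputed to 31 December 2018 and fall outside the window.

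**The case against.** The strongest reply to part 1 is that the TEAE definition itself requires the event to occur after first dose, so an event with an earlier stop date is excluded whatever start date is imputed. Imputation, on this view, fills unknown dates and does not override known ones. A sensible programmer may well read it that way, and a start after its own stop could show up in the listings. But the SAP applies the imputation rules to decide whether an AE is treatment-emergent and states no exception, while 3.6 spells one out for medications. The primary endpoint should not depend on the programmer's judgement.

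On part 2, the SAP governs the tables and its wording is clear. Completers are unaffected for events recorded by Day 98, and subjects who leave the study early may contribute no days beyond 30. SAP section 1 requires only substantial differences to be flagged, and text may have been removed from 3.11. All of this bears on size and on how firmly the disclosure point can be put. It does not remove the conflict between the two definitions.

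It is also fair that the study is blinded, so there is no evident reason for misdated events to favour one arm, and that the calendar shares do not measure how often the error will happen.

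**Conclusion.** The concern holds on both parts, and SAP 3.9.1 is wrong as written. Three of its five imputation branches can turn an event known to be pre-treatment into a TEAE, and its open-ended definition conflicts with protocol 16.1.1 without an entry in the published text of 3.11.

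The size is probably small. Part 1 costs 4 points per misclassified subject in an arm of 25, with an unknown but probably low number of subjects. Part 2 affects mainly early stoppers who remain in follow-up. It hardly moves the headline count, because a subject who stops for intolerance already has a recorded AE; the SOC/PT rows are where it would show. The analysis is descriptive. The change should still be made before lock, because these rules define the primary endpoint. The calendar shares rest on the assumed even spread of first-dose dates; the conclusion does not.

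**What to change.** In SAP 3.9.1:

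- Class an AE whose stop date is before first dose as not treatment-emergent, whatever is known of its start.
- Never impute a start date later than the AE stop date; where the rule would do so, use the stop date. For a partial stop date, apply the exclusion only if every date consistent with it is before first dose.
- Adopt the protocol's window: onset on or after first dose and no more than 30 days after last dose, or worsening of a pre-treatment event. If the open window is intended, list it in 3.11 with a reason, and follow protocol 17.2 on amendments if it is judged a major change.
- If the 30-day limit is restored, impute 1 January instead of 31 December when the recorded year is later than the first-dose year.

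Separately from the SAP error, the protocol uses a 14-day follow-up call (10.1.3.3), 28 days for new SAEs (16.1.1.2) and 30 days for ongoing AEs and for TEAEs (16.1.1.2, 16.1.1). These periods need to be reconciled; this review takes no position on which is right.

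The cost is a few lines of SAP text and programming. It uses dates already collected and needs no new data.

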3.9.2 Clinical Laboratory Evaluation

Blood samples will be collected for routine clinical laboratory safety evaluations at Screening, Baseline, Day 43 (week 6) and Day 84 (week 12). Additional laboratory safety evaluations will be performed at other times, if judged to be clinically

appropriate, or if the ongoing review of the data suggests a more detailed assessment of laboratory safety evaluations is required.

Laboratory parameters include electrolytes, lipids, glucose, renal, hepatic and pancreatic function tests, and hematology.

Clinical chemistry and hematology tests are presented below:

Clinical Chemistry and Hematology Tests

Clinical Chemistry

Albumin
Alkaline phosphatase
Alanine aminotransferase
Aspartate aminotransferase
Bicarbonate
Calcium
Chloride
Cholesterol
Creatine kinase
Creatine, enzymatic
Direct bilirubin
Glucose, random, serum
High density lipoprotein cholesterol
Indirect bilirubin
Lactate dehydrogenase
Low density lipoprotein cholesterol, calculated
Phosphorous
Potassium
Sodium
Total bilirubin
Total protein
Triglyceride
Urea (blood urea nitrogen)
Uric acid
Total cholesterol
Magnesium
Thyroid stimulating hormone

Hematology

Basophils (absolute)
Eosinophils (absolute)
Lymphocytes (absolute)
Monocytes (absolute)
Neutrophils (absolute)
Basophils
Eosinophils
Hematocrit
Hematology slide
Hemoglobin
Lymphocytes
Monocytes
Neutrophils
Platelets
Red blood cells
White blood cells

Continuous laboratory data will be examined for trends using descriptive statistics of actual values and changes from baseline over time. These data will also be categorized as low, normal or high based on the reference ranges of the central

laboratory. Shift tables from baseline to each post baseline time point will be presented.

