11.3 Exclusion Criteria

A subject will NOT be eligible for this study if any of the following criteria apply:

1. Non-ambulatory subjects (e.g. requiring a wheelchair) not able to perform the assessments of Motor Ability/Function
2. Poorly controlled seizures defined as > 3 seizures lasting less than 3 minutes per week or > 1 seizure episode lasting more than 3 minutes per week or as per medical monitor judgment
3. Concomitant cardiovascular or respiratory diseases of a degree that would limit participation in the study
4. Concomitant disease (e.g., gastrointestinal, renal, hepatic, endocrine or cardiovascular system disease) or condition or any clinically significant finding at screening that could interfere with the conduct of the study, or that would pose an unacceptable risk to the subject in this study
5. Any of the following laboratory abnormalities: total bilirubin >1.5 x upper limit of normal (ULN) (unless isolated Gilbert's syndrome), alanine aminotransferase or aspartate aminotransferase >2.5 x ULN; serum creatinine >1.2 x ULN; absolute neutrophil count <1.5 x 10⁹/L, platelets < 80 x10⁹/L, hemoglobin <80 g/L; TSH >1.25 x ULN or <0.8 x ULN
6. Pregnancy
7. Women of child-bearing potential who are not using a double-barrier method of contraception (e.g. condoms plus oral contraceptives), with abstinence being an accepted method
8. Concomitant use of minocycline, levodopa, zolpidem, zaleplon, eszopiclone, ramelteon or benzodiazepines for sleep, as well as, cannabinoid derivatives, and any other use of any investigational agent, device, and/or investigational procedure 4 weeks prior to Baseline and during the study
9. Allergy to OV101 or any excipients
10. At increased risk of harming self and/or others based on investigator assessment
11. Any condition or reason that in the opinion of the investigator, makes the subject unsuitable for enrollment
12. Inability of subject or caregiver to comply with study requirements

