13.1.2 Discontinuation of Study Drug

If it is necessary to discontinue the study drug earlier than planned, subjects should continue to be followed per protocol to capture safety and efficacy assessments for the duration of the study period if feasible.

The investigator may withdraw the subject from the study drug for the following reasons:

- Upon subject's or caregiver's request
- The subject or caregiver is unwilling or unable to adhere to the protocol-specified visits
- The subject experiences an intolerable AE
- During the study, the subject develops symptoms or conditions listed in the exclusion criteria
- Other medical reason, at the discretion of the investigator and/or the Medical Monitor

Subjects who discontinue the study due to an AE considered related to study drug should be followed until the event is resolved, considered stable, or the investigator determines the event is no longer clinically significant. Study drug discontinuation due to AEs considered not related to study drug will be followed until resolution.

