16.1.1.2 Recording of Adverse Events

For the purposes of this study, any detrimental change in the subject's condition, from the screening visit (Day -28) and up to completion of the follow-up period after the last administration of study drug (Day 98 follow-up phone visit) should be considered an AE and must be recorded on the eCRF.

All SAEs and AEs will be recorded starting from the screening visit (Day -28).

All ongoing AEs should be followed up for 30 days after the last administration of study drug, with the exception of any ongoing study drug-related AEs, which should be followed until resolution, unless in the investigator's opinion, the AE is unlikely to resolve due to the subject's underlying disease. Any new SAEs occurring up to 28 days after the last administration of study drug (Day 98 follow-up phone visit) should be reported according to Section 16.1.1.6.

At any time after the follow-up visit, if an investigator learns of an SAE that can be reasonably related to study drug, he/she should promptly notify Ovid Therapeutics Inc.

The severity of AEs and SAEs will be graded using the National Cancer Institute Common Terminology Criteria for Adverse Events (CTCAE, Version 4). Any AE not listed in the CTCAE will be graded as follows:

| Severity Grade | Definition |
|----------------|------------------------------------|
| 1 | Mild AE |
| 2 | Moderate AE |
| 3 | Severe or medically significant AE |
| 4 | Life-threatening AE |
| 5 | Death related to AE |

It is important to distinguish between serious and severe AEs. Severity is a measure of intensity whereas seriousness is defined by the criteria in Section 16.1.1.

An AE of severe intensity need not necessarily be considered serious. For example, nausea that persists for several hours may be considered severe nausea, but not an SAE. On the other hand, a stroke that results in only a limited degree of disability may be considered a mild stroke but would be an SAE.

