17.2.4.1 Safety Analysis

All AEs will be coded using MedDRA Dictionary Version 19.1 and will be classified by MedDRA system organ class (SOC) and preferred term (PT).

The number and percentage of subjects who experience at least one TEAE and the number and percentage of subjects who experience at least one TEAE within each specific SOC and PT will be presented by treatment group. The 95% CIs will be displayed for the frequency of TEAEs. Treatment-related AEs will be considered those at least possibly related to investigational product based on the investigator's assessment. The number and percentage of subjects reporting serious AEs, treatment-related AEs, and AEs leading to treatment discontinuation will also be summarized for each treatment group by MedDRA SOC and PT.

Descriptive statistics for laboratory values and vital signs at each time point will be summarized by treatment group. Clinically significant laboratory values may be tabulated by treatment group.

Shift tables for laboratory parameters will be presented to show the change of normality from Baseline to each post baseline visit. For each continuous laboratory parameter, results will be categorized as low, normal, or high based on the laboratory normal ranges. Frequencies and percentages will be presented by treatment arm for the shifts in these categories (i.e., low to normal, low to high, high to low, etc.) from baseline to each post-treatment assessment time point.

Tables and graphical displays (such as scatter plots of baseline versus worst post-baseline values) of key safety parameters may be generated to better understand the study drug safety profile.

Concomitant medications will be coded using the World Health Organization Drug Dictionary. A table summarizing concomitant medications and by-subject listing of concomitant medications will include all medications taken during the study regardless of the timing for the start of the medication.

17.2.4.2 [REDACTED]

[REDACTED]

[REDACTED]

[REDACTED]

[REDACTED]

17.2.4.3

A thick black horizontal bar with a small black square at the right end.

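### SAP laboratory shift tables use only low/normal/high at each visit, so marked worsening can score as unchanged and no table counts subjects with marked abnormalities by arm

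*SAP*

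**What the plan says.** SAP 3.9.2 plans two things for laboratory data: descriptive statistics of values and changes from baseline, and a categorical analysis. On the categories it says "These data will also be categorized as low, normal or high based on the reference ranges of the central" laboratory, and then "Shift tables from baseline to each post baseline time point will be presented". The SAP table list carries four laboratory tables (14.3.2.1.1, 14.3.2.1.2, 14.3.2.2.1 and 14.3.2.2.2): a summary and a shift for chemistry, and the same for hematology. The numbering runs straight on to 14.3.3 (vital signs), and the redactions in the list fall in the efficacy block. No laboratory title mentions grades, multiples of ULN or a worst value.

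Protocol 17.2.4.1 uses the same three classes: "results will be categorized as low, normal, or high based on the laboratory normal ranges". It adds, as an option, "Clinically significant laboratory values may be tabulated by treatment group", with no threshold, and also allows plots of baseline against the worst later value. The readable SAP takes up neither.

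Protocol 11.3, criterion 5, sets the entry limits, among them "alanine aminotransferase or aspartate aminotransferase >2.5 x ULN; serum creatinine >1.2 x ULN". It also bars total bilirubin above 1.5 x ULN (isolated Gilbert's syndrome exempt), TSH above 1.25 x ULN, neutrophils below 1.5 x10^9/L, platelets below 80 x10^9/L and hemoglobin below 80 g/L. Protocol 13.1.2 lists, among the reasons for which the investigator may withdraw a subject from study drug, "During the study, the subject develops symptoms or conditions listed in the exclusion criteria".

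SAP 4.1.1 says that when a post-baseline visit has several results for one assessment, the first is analyzed. SAP 3.9.2 allows additional laboratory tests at unscheduled times.

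**The concern.** The entry limits lie outside the reference range, so a subject can enroll between the two. Such a subject is already high (or low) at baseline and has no worse category to move to. For a subject who starts normal, the shift table separates normal from high but not a trivial excess from a large one.

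Laboratory parameters are listed under the primary safety objective (protocol 9.1), and laboratory shift is a safety endpoint in its own right (SAP 3.3.3). A reader of the shift tables would see slight crossings of the reference limit counted, and could not tell how many subjects in each arm had a marked abnormality. A worse repeat at the same visit is set aside by the first-record rule, and an unscheduled value has no specified place in a shift laid out by scheduled time point.

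**Working it through.** **1. The plan's own safety figure, for context.** Protocol 17.1 gives 95% CI half-widths of 17% (n = 25) and 19% (n = 20) at a true incidence of 25%. Wald half-width = 1.96 x sqrt(0.25 x 0.75 / n) = 0.1697 and 0.1898. Both reproduce. The point below does not depend on them.

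**2. Classification of illustrative values.** The cut-offs are the SAP classes and the criterion-5 limits. ALT/AST, bilirubin, creatinine and TSH are in multiples of ULN. The documents give no reference ranges, so the lower limits of normal are assumed: hemoglobin 120 g/L, platelets 150 x10^9/L, neutrophils 1.8 x10^9/L. The low-side results hold for any lower limit above the baseline value shown.

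| Analyte | Baseline to later value | SAP shift cell | Passes criterion-5 limit? |
|---|---|---|---|
| ALT/AST | 1.1 to 2.4 | high to high | no |
| ALT/AST | 1.1 to 10 | high to high | yes (2.5) |
| ALT/AST | 2.4 to 10 | high to high | yes (2.5) |
| ALT/AST | 1.0 to 1.1 | normal to high | no |
| ALT/AST | 1.0 to 10 | normal to high | yes (2.5) |
| Bilirubin | 1.4 to 3 | high to high | yes (1.5) |
| Creatinine | 1.15 to 2.5 | high to high | yes (1.2) |
| TSH | 1.2 to 3 | high to high | yes (1.25) |
| Hemoglobin | 85 to 60 | low to low | yes (80) |
| Platelets | 90 to 40 | low to low | yes (80) |
| Neutrophils | 1.6 to 0.8 | low to low | yes (1.5) |

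The first three rows share a cell, and so do the fourth and fifth. The shift table cannot separate them.

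**3. What the continuous summaries would show.** Suppose one of 25 subjects goes from 2.0 to 8.0 x ULN and the other 24 do not change (an assumption).
- Mean change = (8.0 - 2.0)/25 = 0.24 x ULN.
- SD of change = sqrt{[(6 - 0.24)^2 + 24 x 0.24^2]/24} = sqrt(34.56/24) = 1.2 x ULN.
- Maximum value = 8.0 and maximum change = 6.0 x ULN.

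The mean barely moves, while the SD, the maximum value and the maximum change respond. None of them says how many subjects were affected.

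**4. What a count could show.** One subject in 25 is 4%. The chance of seeing at least one case is 1 - (1 - p)^n, with p assumed:

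| True rate p | n = 25 | n = 50 (combined OV101) |
|---|---|---|
| 2% | 40% | 64% |
| 5% | 72% | 92% |
| 10% | 93% | 99.5% |

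With no case observed, the exact two-sided 95% upper limit is 1 - 0.025^(1/n): 13.7% for 0/25 and 7.1% for 0/50. The counts would be small and descriptive, but readable by arm.

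**The case against.** The strongest reply is that the safety plan as a whole does react to a marked abnormality. SAP 3.1 gives SD, quartiles and extremes by arm and lists all data by subject, and with about 25 subjects per arm the listings can be read in full. Under protocol 16.1.1.3 a laboratory abnormality should be reported as an adverse event if it meets a seriousness criterion, leads to discontinuation, interruption or dose modification, or is thought reportable by the investigator. SAP 3.9.1 then counts such events by arm, including those leading to discontinuation (Table 14.3.1.7). All of this stands. A reader might infer that marked abnormalities would go unseen, or that only the maximum would reveal them; the documents support neither reading. The gap that remains is narrower. Adverse event capture rests partly on judgment (protocol 16.1.1 says abnormal values are not usually treated as adverse events), and extremes and listings are not counts.

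Four other stronger readings also fail:
- **That criterion 5 sets on-treatment limits.** It is an eligibility rule, and 13.1.2 gives it only a permissive role during the study.
- **That the protocol calls for laboratory values to be graded.** Section 16.1.1.2 adopts CTCAE version 4 for the severity of adverse events only.
- **That the SAP drops a protocol commitment.** The protocol specifies the same three classes, and its extra table and plot are optional. The SAP's list of figures shows no entries, so the absence of a plot from it proves nothing.
- **That harm is demonstrated.** The worked values are invented, and the readable text describes no laboratory signal from prior use.

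**Conclusion.** The point holds as a gap in the tabulation, not as an error, a contradiction or an unmet commitment. Three classes by visit cannot show the size of a worsening. They record no shift for a subject who enters out of range and worsens in the same direction, and no planned laboratory table counts subjects with a marked abnormality by arm. The first-record rule and the per-visit layout can also leave the worst value out of the shift.

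The masking follows from the definitions alone; the low-side examples also need a lower reference limit above the baseline value. How often it would occur cannot be computed, because the documents do not say how many subjects enter out of range. The conclusion rests on the readable SAP text and on the laboratory table list, which shows no redaction or gap. The change is a cheap improvement worth making.

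**What to change.** Add one table to SAP 3.9.2 and the table list: n (%) of subjects in each arm (QD, BID, combined OV101, placebo) with any post-baseline value beyond each numeric criterion-5 limit.

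- Say that the limits serve as descriptive cut-offs and not as treatment rules.
- Include unscheduled and repeat results, stated as an exception to SAP 4.1.1.
- Split by whether the baseline value was within or outside the reference range. A split by whether the limit was already exceeded at baseline would be nearly empty, since such subjects are generally excluded; footnote any that occur, for example under the Gilbert's exemption.
- Leave out the TSH lower limit for now. It is written as below 0.8 x ULN, a multiple of the upper limit, so taken literally it would count values inside the reference range. The sponsor must reconcile it first.
- Confirm that the creatine (enzymatic) entry in the laboratory list is the creatinine measure named in criterion 5.

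Keep the existing low/normal/high tables. A shift from baseline to worst value by CTCAE version 4 grade is optional; its cut-offs are in neither document and would have to be specified.

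Cost: SAP wording and one output from data already collected. The downside is slightly more output, with small counts that support description only.
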